4.5 EXPLORATORY ENDPOINT(S) ANALYSIS

4.5.1 Definition of endpoint(s)

The definition of exploratory endpoints are summarized in [Table 2](#) with details provided below

- The kidney disease quality of life instrument - 36 items (KDQOL-36) is a patient-reported disease-specific measure of health-related quality of life. The KDQOL-36 includes the Medical Outcomes Study’s 12-Item Short-Form Health Survey (SF-12) as a generic core and the 24-item kidney disease targeted questionnaire. The items of the SF-12 are summarized into the Physical Component Summary (PCS) score and the Mental Component Summary (MCS) with response alternatives varying from 2- to 6-point scales. The kidney disease targeted instrument includes three scales: Symptoms and Problems (12 items), Burden of Kidney Disease (4 items), and Effects of Kidney Disease (8 items); all items have 5 response options. The scale scores of the KDQOL-36 questionnaire (PCS, MCS, symptoms and problems, burden of kidney disease, effects of kidney disease,) are transformed to 0 to 100 with higher scores indicating better HRQOL. KDQOL-36 will be administered to adults only and every 12 weeks during Stage 2 placebo-controlled

treatment period. For the SF-12 analysis purpose, the scoring will be provided by QualityMetric Inc, based on Scoring Software Version 4.5 of the SF-12v2 Health Surveys.

- The PedsQL scale is a brief, standardized, generic assessment instrument that systematically assess patients' and parents' perceptions of health-related quality of life in pediatric patients with chronic health conditions. The PedsQL consists of a 23-item core measure, which includes a child self-report for patients aged 5 to 18 years. The 23-item PedsQL Generic Core Scales include four Scales, Physical Functioning (8 items), Emotional Functioning (5 items), Social Functioning (5 items), and School Functioning (5 items).
- The PGIC is a two-item questionnaire (one item evaluating fatigue and the other hearing loss) evaluated on a 7-point Likert scale designed to assess patients' reported evaluation of change in their disease overall in regard to the start of study medication. This aims at evaluating the change in symptoms since the beginning of the study. The participant must select from the response of the options that denotes the most accurate description of his/her change in state of health (overall status) ranging from 'Very much better' to 'Very much worse'.
- The PGIS is a two-item questionnaire (one assessing fatigue and the other hearing loss) evaluated on a 5-point Likert scale designed to assess patients' reported evaluation of severity in their symptoms. The participant must select from the response of the options that denotes the most accurate description of his/her change in state of health (overall status) ranging from 'No [symptom]' to 'Very severe [symptom]'.
- Hearing will be assessed during the Treatment Period and Extension open-label Period using a pure tone audiometry (air only) test at defined frequencies. At baseline, Week 48 and Week 96, hearing will be measured at right and left ear. Degrees of hearing level will be derived as follows:
 - All possible hearing results will be converted to numerical value as follows: Normal hearing=0, mild hearing loss=1, moderate hearing loss=2, severe hearing loss=3, profound hearing loss=4.
 - The hearing results from right and left ears will be added up so that degrees of hearing level in both ears ranges from 0 (indicating normal hearing for both ears) to 8 (profound hearing loss for both ears).

4.5.2 Main analytical approach

[figure not shown]
For the exploratory endpoints that are patient-reported outcomes, the main analytical approaches are discussed in [Section 4.8.3](#). For the tertiary/exploratory biomarker endpoint, the analyses approaches are described in [Section 4.8.4](#). For the rest of the tertiary/exploratory endpoints, the main analytical approaches are described below.

For time to reach the composite endpoint for the secondary population, the same statistical analyses method as described in [Section 4.4.1.2.3](#) will be used. The only exception is that patients with screening eGFR ≤ 35 mL/min/1.73 m² will be included.

Change from baseline at Week 48 and Week 96 of double blind placebo-controlled treatment period, respectively in degrees of hearing level recorded in both ears measured by a pure tone audiometry will be analyzed with analysis of covariance (ANCOVA) with treatment, screening eGFR stratification factor, age category (<18 versus \geq 18 years old), SGLT2 inhibitor treatment at screening (versus those without) as covariates.

The shift in overall hearing assessment results in both ears (normal hearing, mild, moderate, severe, and profound hearing loss) from baseline to Week 48 and 96 will be summarized.

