- b After Day 1, the visits will be done every 7 days. During the active treatment period, the visit window is ±2 days for each visit. Subjects who complete the double-blind, placebo-controlled treatment period will be rolled over directly into the open-label treatment extension (see Table 2). Subjects who complete the double-blind, placebo-controlled treatment period but who will not continue with the open-label treatment extension will enter the follow-up period, which is the same for all subjects.
- c Except for complete blood count (CBC), serum and urine chemistry, and coagulation panel, laboratory tests scheduled for the early termination (ET) visit do not need to be completed if the tests were completed as part of a study visit within 4 weeks of the last visit. ET will be done 7 days ±2 days after the last study visit.
- d Follow-up days and weeks are numbered starting from the last scheduled visit in the active treatment period. Thus, for subjects who discontinue early, Follow-up Week 2 is 2 weeks after the ET visit. The visit window is ±3 days for all follow-up visits.
- e For subjects who complete the double-blind, placebo-controlled treatment period and will enter the open-label treatment extension, the Week 48 visit will serve as the baseline visit of the open-label extension.
- f Day 1 is the baseline visit.
- g See Section 5 for visit windows, and Section 5.2 for odds visit details.
- h Option for Investigator to delegate visit assessments to be performed at an alternate location, including the subject’s home, conducted by trained, qualified study personnel. During the last 6 months of the double-blind period, the subject will be trained on self-administration of the study drug and will be observed in self-administration technique.
- i Informed consent will be obtained prior to performing any study-related procedures.
- j Prior and ongoing illnesses, surgeries, use of tobacco/alcohol/recreational drugs, and allergic reactions/hypersensitivity.
- k Family history relevant to Alport syndrome and renal disease.
- l Prior medication/therapy is any medication or therapy given within 30 days before study entry (eg, before signing the informed consent form [ICF]), as well as ongoing medication or therapy.
- m Any medication taken after signing the ICF will be collected at each visit.

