6.2.13 Hearing assessment

Hearing will be assessed during the Treatment Period and Extension Period using a pure tone audiometry (air only) test at defined frequencies at baseline, Week 48 and 96.

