ITT population	To assess the effect of lademirsen on urine and blood biomarkers in Alport Syndrome participants.	Changes in exploratory biomarkers from baseline at Weeks 24 and 48 during the placebo-controlled treatment period: 
 In both blood and urine^b: β-2 microglobulin and connective tissue growth factor (CTGF) In urine only^b: kidney injury molecule-1 (KIM-1)/creatinine ratio and calbindin-D28k/creatinine ratio
ITT population	To assess the efficacy of lademirsen in reducing the decline in hearing sensitivities at Week 48.	Change from baseline at Week 48 in degrees of hearing level recorded in both ears measured by a pure tone audiometry in the placebo controlled treatment period

^a The definition of population is in [Table 2](#).

^b Urine biomarkers will be standardized by creatinine before analysis. If the urine parameter is collected through 24-hour urine, then the standardized value will be calculated by the original value divided by 24-hour urine creatinine; else if the urine parameter is collected through instant urine, then the standardized value will be calculated by divided by instant urine creatinine.

^c This is one of the primary objectives for Amended Protocol 11 and 12, and secondary objective for Amended Protocol 13.

Table 2 - Populations for analyses

Population	Description
Randomized population	All randomized participants. Participants will be analyzed according to the study intervention allocated by randomization.
ITT population	All randomized participants. Participants will be analyzed according to the study intervention allocated by randomization.
Compliant ITT population	All randomized participants who received $\geq 80\%$ planned IMP during the double-blinded, placebo-controlled treatment period Participants will be analyzed according to the intervention allocated by randomization.
Primary population	All randomized participants who completed the double-blinded period (the first 48 weeks) or discontinued double-blinded period early. Participants will be analyzed according to the study intervention allocated by randomization.
Compliant primary population	All randomized participants who completed the double-blinded period (the first 48 weeks) or discontinued double-blinded period early, and received $\geq 80\%$ planned study intervention during the double-blinded treatment period Participants will be analyzed according to the study intervention allocated by randomization.

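### The Week 48 hearing ANCOVA leaves out the pre-dose hearing score, which gives up some precision and leaves the estimate open to any baseline imbalance that is observed

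*SAP*

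**What the plan says.** **Outcome.** SAP 4.5.1 grades each ear as "Normal hearing=0, mild hearing loss=1, moderate hearing loss=2, severe hearing loss=3, profound hearing loss=4" and adds the two ears, giving an integer from 0 to 8. It schedules the measurement: "At baseline, Week 48 and Week 96, hearing will be measured at right and left ear".

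**Model.** SAP 4.5.2 says that change from baseline in this score "will be analyzed with analysis of covariance (ANCOVA) with treatment, screening eGFR stratification factor". After age category, the list closes with "SGLT2 inhibitor treatment at screening (versus those without) as covariates". Baseline hearing is not in it. The same section plans a summary of shifts between hearing categories from baseline.

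**What the addendum keeps.** Table 1 of the SAP addendum (section 3) lists "Change from baseline at Week 48 in degrees of hearing level recorded in both ears measured by a pure tone audiometry" as an exploratory endpoint in the ITT population. Section 3 reports no major change of statistical method and drops covariates relevant only to Stage 2, without naming them.

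**Availability of the baseline.** Protocol 6.2.13 requires audiometry "using a pure tone audiometry (air only) test at defined frequencies at baseline, Week 48 and 96". A footnote to protocol Table 1 says "Day 1 is the baseline visit". Protocol 5.2 puts the hearing assessment among the tests done before the first injection. SAP 5.2.1 lists each ear's hearing result as a baseline disease characteristic.

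**Comparison within the SAP.** The FACIT-F model in SAP 4.4.1.2.4 names the baseline value as a fixed effect.

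**The concern.** A participant who scores 0 at baseline can only stay or worsen, and one who scores 8 can only stay or improve. Values near a category boundary tend to move back towards the mean. Change in this score therefore depends on where the participant started.

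Stage 1 randomisation was stratified by screening eGFR only (SAP 1.1), so nothing in the design balances hearing. Hearing loss is one of the features of the clinical diagnosis in inclusion criterion I 02, so baseline scores can be expected to vary. If the arms differ at baseline by chance, an unadjusted comparison of change carries part of that difference into the treatment estimate. What is at stake is how the one inferential hearing comparison in the final analysis is read, and some of its precision.

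**Working it through.** The documents give no power, SD or correlation for hearing, so there is no stated figure to reproduce.

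**Inputs from the documents**
- 43 participants randomised 2:1 in Stage 1 (SAP 1.1). I take this as 29 vs 14. The realised split is not stated.
- The study stopped before all Stage 1 participants had completed the double-blind period (addendum section 3), so fewer than 43 will have Week 48 data.

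**Assumptions**
- r, the correlation between baseline and Week 48 scores, from 0.7 to 0.95.
- For the closed forms, the same SD at both visits. SD_b is the baseline SD.

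**Step 1. How large is a chance imbalance?**
SD of the baseline difference between arms = SD_b × sqrt(1/29 + 1/14) = 0.325 SD_b.
P(|imbalance| > 0.5 SD_b) = 2 × [1 − Φ(0.5/0.325)] = 12.4%.

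**Step 2. How far does an observed imbalance move the unadjusted estimate?**
Conditional shift = −(1 − r) × imbalance. The standard error of the change contrast is sqrt(2(1 − r)) × 0.325 SD_b. For an imbalance of one standard error (0.325 SD_b), the ratio of shift to standard error is sqrt((1 − r)/2).

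**Step 3. How much variance does adjustment remove?**
Var(adjusted)/Var(change) = (1 + r)/2.

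| r | Shift per 0.5 SD_b imbalance | Shift for a 1-SE imbalance, in SEs of the estimate | Variance ratio |
|---|---|---|---|
| 0.95 | 0.025 SD_b | 0.16 | 0.975 |
| 0.9 | 0.05 SD_b | 0.22 | 0.95 |
| 0.8 | 0.10 SD_b | 0.32 | 0.90 |
| 0.7 | 0.15 SD_b | 0.39 | 0.85 |

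**Step 4. Does this hold on the bounded integer scale?**
Null simulation with no treatment effect, 29 vs 14, 8,000 trials per setting. Each ear is graded 0 to 4 from an assumed normal latent value (mean 1.3, SD 1.2 grades), with assumed noise SD of 0.2, 0.4 or 0.7 grades and a drift of 0.1 grade. Change is analysed with treatment and a two-level stratum, with and without the baseline score. The conditional columns cover trials in which the first arm's baseline mean was at least 1 point higher, 7.7% of trials in each setting (mean imbalance about 1.3 points).

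| r obtained | Mean estimate, all trials, unadjusted | Given imbalance: unadjusted | Given imbalance: adjusted | SE unadjusted | SE adjusted |
|---|---|---|---|---|---|
| 0.94 | 0.000 | −0.050 | +0.006 | 0.248 | 0.250 |
| 0.87 | 0.006 | −0.146 | −0.027 | 0.383 | 0.382 |
| 0.71 | 0.007 | −0.307 | −0.013 | 0.573 | 0.557 |

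Three things follow.
- Over all trials the unadjusted estimate centres on zero, so there is no bias over repeated randomisation.
- Given an imbalance, the unadjusted estimate moves and the adjusted one returns to within about 0.03 points of zero.
- The closed forms are somewhat generous on this scale. At r = 0.71 the formula predicts a shift of (1 − 0.714) × 1.31 = 0.37 points, against 0.31 simulated. The simulated variance ratios are (0.250/0.248)² = 1.02, (0.382/0.383)² = 0.99 and (0.557/0.573)² = 0.94.

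A separate simulation, starting from decibel thresholds with assumed cut-points, baseline means and test-retest SDs and a 28 vs 15 split, gave variance ratios of 0.89 to 1.00.

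**The case against.** The strongest reply is that randomisation already protects this comparison. That is correct. A reader might infer that the planned analysis is biased, and the documents do not support that: allocation is randomised, and the simulated null means are 0.000 to 0.007. The shift exists only conditional on an imbalance that has actually occurred. Nor do the documents support saying that a material imbalance is likely. On a 29 vs 14 split, one above half a baseline SD occurs about one time in eight.

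The second reply is that the gain may be negligible. This also stands in part. If hearing grades are stable over 48 weeks (r near 0.9 or above), the two standard errors are almost equal and the shift is small.

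The third is that an imbalance would be seen, because the baseline tables show hearing by ear and a shift summary is planned. Both make an imbalance visible, but neither adjusts the arm comparison.

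The fourth is that the term ANCOVA may imply a baseline covariate. The SAP spells out its covariate lists, and where it wants the baseline value, as for FACIT-F, it names it. At best the hearing text is ambiguous.

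Last, the endpoint is exploratory, the addendum plans no multiplicity adjustment, and the study had already been terminated after the futility analysis. All true, and these facts fix the weight of the point. None is a reason to prefer the model without baseline.

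**Conclusion.** The point holds as a small improvement to an exploratory analysis. The retained hearing model omits a pre-dose measurement of its own outcome that the trial already collects. The consequence is a conditional shift of a fraction of a standard error (about 0.16 to 0.39 for a one-standard-error imbalance) and a variance penalty between nothing and about 15%, with the bounded-scale simulations towards the lower end.

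These sizes rest on an assumed r of 0.7 to 0.95, an assumed score distribution, and a 29 vs 14 split that overstates the Week 48 sample. Fewer participants would make imbalance more likely, not less.

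It should not be read as a flaw in the primary analysis. The eGFR slope comparison does not involve hearing, and its conclusion is unaffected.

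**What to change.** In the addendum, state the full Week 48 hearing model: change in the summed score on treatment, screening eGFR stratum and the baseline summed hearing score (0 to 8). Name the dropped covariates as well. Age category and SGLT2 inhibitor use are inferred to be the Stage 2-only terms, because Stage 1 enrolled adults aged 18 to 55 and SGLT2 use was a stratification factor only in Stage 2. The addendum does not say so. Keep the shift summary.

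The cost is one model term and one residual degree of freedom: with all 43 participants, from 43 − 3 = 40 to 39 (intercept, treatment and a two-level stratum, then baseline). No new data are needed. If the database is already locked, report the adjusted model as a labelled sensitivity analysis beside the planned one.

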4.7 SAFETY ANALYSES

For safety analyses, other than the analysis for **placebo-controlled treatment** period, the analyses for **lademirsen treatment period** and **overall study treatment period** are discussed both in this section and [Section 4.8.5](#).

4.7.1 Extent of exposure

The extent of IMP exposure during placebo-controlled period and overall study period will be assessed and summarized by actual treatment within the safety population. The extent of IMP exposure during lademirsen treatment period will be assessed and summarized by actual treatment within the lademirsen treated population.

4.7.1.1 Extent of investigational medicinal product exposure

The extent of IMP exposure will be assessed by the duration of IMP exposure and compliance, and actual dose information.

Duration of IMP exposure

Duration of IMP exposure in **placebo-controlled period**, will be summarized descriptively as a quantitative variable that number of participants, mean, SD, median, minimum, and maximum will be provided. In addition, duration of treatment exposure will also be summarized categorically by numbers and percentages for each of the following categories and cumulatively according to these categories: >0 and ≤12 weeks, >12 and ≤24 weeks, >24 and ≤36 weeks, ... (by every 12 weeks), and up to the last available study week during the defined treatment period.

Additionally, the cumulative duration of treatment exposure will be provided, defined as the sum of the duration of treatment exposure for all participants in placebo-controlled period, and will be expressed in patient years.

The duration of IMP exposure/cumulative duration of exposure **in lademirsen treatment period** and **in overall study period** will summarized similarly. The following categories of duration of treatment exposure will be presented: >0 and ≤12 weeks, >12 and ≤24 weeks, >24 and ≤36 weeks, ... (by every 12 weeks), and up to the last available study week during the defined treatment period.

4.7.1.2 Compliance

A given administration will be considered noncompliant if the participant did not take the planned number of administrations as required by the protocol. No imputation will be made for participants with missing or incomplete data.

In **placebo-controlled treatment period**,

- **Percentage of compliance** for a participant is defined as the number of administrations that the participant was compliant (eg, the dose level of actual received is the same as planned) divided by the total number of administrations that the participant was planned during the placebo-control period.
- **Above-planned dosing percentage** for a participant is defined as the number of actual administrations the participants received with a dose level higher than planned (eg, the planned dose is 110 mg for adult however the actual received dose is 120 mg; or the planned dose is 75 mg [=1.5 mg/kg *50 kg] for an adolescent weighted 50 kg, however, the actual received dose is 160 mg) divided by the total number of administrations that the participant was planned during the placebo-control period.

- **Under-planned dosing percentage** for a participant is defined as the number of actual administrations with a lower dose level (eg, the planned dose is 110 mg for adult however the actual received dose is 90 mg or the planned dose is 75 mg [=1.5 mg/kg *50 kg] for an adolescent weighted 50 kg, however, the actual received dose is 100 mg) or even omitted (eg, drug administration at Week xx is planned however not administrated) than planned divided by the total number of administrations that the participant was planned during the placebo-control period.

In lademirsen treatment period,

- **Percentage of compliance** for a participant is defined as the number of administrations that the participant was compliant (eg, the dose level of actual is the same as planned) divided by the total number of administrations that the participant was planned to take during the lademirsen treatment period.
- **Above-planned dosing percentage** for a participant is defined as the number of actual administrations the participants received with a dose level higher than planned divided by the total number of administrations that the participant was during the lademirsen treatment period.
- **Under-planned dosing percentage** for a participant is defined as the number of actual administrations with a lower dose level or even omitted (eg, drug administration at Week xx is planned however not administrated) than planned divided by the total number of administrations that the participant was planned during the lademirsen treatment period.

Treatment compliance, above-planned, and under-planned dosing percentages, will be summarized descriptively as quantitative variables (number, mean, SD, median, minimum, and maximum). The percentage of participants whose compliance is <80% and ≥80% will be summarized. In addition, participant numbers and percentages of participants with 0, (0, 20%], and >20% above/under-planned dose administrations will be summarized. All above will be summarized for the analyses during both double-blind treatment period and lademirsen treatment period, respectively.

Number of participants with dose reduction (eg, the schedule of drug administration changed from weekly to bi-weekly) during placebo-controlled treatment period will be summarized in total, by the initiation visit of dose reduction categories as Week 1 - 12, Week 13 - 24, ... (by every 12 weeks), and up to the last available study week during the defined treatment period.

Number of participants with at least one dose omission (eg, drug administration at Week xx is planned however not administrated) during placebo-controlled treatment period will be summarized in total and by the following number of omitted doses categories as 1 - 4, 5 - 8,... (by every 4 doses), and up to maximum allowed dose during the defined treatment period.

The number of participants with dose reduction and at least one dose omission during the lademirsen treatment period will be summarized similarly by extending the categories to the last available study week during the defined treatment period.

A listing of exposure to investigational product of each participant during the overall study period will be provided.

